### **1.2 Study Design (Protocol Version 2.0)**

This study is a randomized, double-blind, placebo-controlled non-inferiority trial designed to assess the overall safety and toxicity of 28 weeks of isoniazid (INH) preventive therapy (IPT) initiated during pregnancy versus deferred initiation of IPT at 12 weeks postpartum in HIV-infected pregnant women and their infants at high risk for TB infection and disease. The study will also assess the efficacy of these strategies in the women and their infants, safety and toxicity of INH *in utero* and on infants, INH resistance among *Mycobacterium tuberculosis* (*M.tb.*) isolates among participants who develop TB while on study, intensive PK of INH and ARV drugs among HIV-infected women on HAART, adherence to INH during pregnancy and postpartum, and performance characteristics of IGRA with TST among HIV-infected pregnant women and their infants.

A target of 950 HIV-infected pregnant women at  $\geq 14$  to  $\leq 34$  weeks (34 weeks, 6 days) of gestation and living in high TB incidence areas, defined as having 60 TB cases per 100,000 population in the WHO TB annual report, will be enrolled. Women who are suspected of having TB with a positive WHO TB symptom screen, have reported recent exposure to an active TB case, have received INH or TB treatment for  $>30$  days in the past year, have evidence of acute hepatitis within 90 days prior to study entry, or have  $\geq$ Grade 1 peripheral neuropathy will not be eligible.

Participants will be stratified based on gestational age at entry, and will be randomized in equal proportions to one of the following two groups:

- ARM A: Maternal INH at study entry for 28 weeks and then switched to placebo for INH until 40 weeks postpartum (immediate IPT), or
- ARM B: Maternal placebo for INH from study entry until 12 weeks postpartum and then switched to INH for 28 weeks until 40 weeks postpartum (deferred IPT)

Each maternal participant will also receive vitamin B6 and multivitamins from study entry until 40 weeks postpartum, as well as intensified TB case finding, and will be followed up to 48 weeks postpartum. Each infant participant will be followed from birth until 48 weeks postpartum with

intensified TB case finding.

The primary hypothesis is that initiation of IPT during pregnancy among HIV-infected pregnant women is as safe as deferring IPT to 12 weeks postpartum.

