### **2.2 Secondary Objectives**

1. To compare safety and toxicity of INH *in utero* exposure and on infants on study
2. To compare TB incidence and all-cause mortality in HIV-infected women and their infants enrolled on study
3. To compare overall safety and hepatotoxicity, as well as evaluate risk factors for these outcomes, during pregnancy and immediate postpartum in women on immediate versus deferred INH therapy
4. To evaluate for INH resistance among *M.tb.* isolates from HIV-infected women and infants who develop TB while on study
5. To evaluate the intensive pharmacokinetics of INH and selected ARV drugs in a subset of HIV-infected pregnant and postpartum women receiving HAART
6. To evaluate and compare the performance characteristics of IGRA (TB ELISPOT and QGIT) with TST in HIV-infected women and their infants
7. To compare adherence in women initiating immediate versus deferred INH preventive therapy via self-report and pill counts

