### **3.2 Secondary Endpoints**

- ***In utero* exposure and infant endpoints:**
  - Fetal death
  - Small for gestational age
  - Premature birth (< 37 weeks gestation)
  - Low birth weight (< 2500 gm)
  - Congenital anomalies
  - Grade 3 or higher clinical or laboratory AEs
    - ◆ all AEs
    - ◆ possibly, probably, or definitely related to INH/Placebo for INH
  - HIV infection
  - Hospitalization
- **Any of the following endpoints:**
  - Maternal TB (probable or confirmed – see Appendix 100 for definitions)
  - Infant TB (probable or confirmed, as defined in Appendix 100, and congenital TB, as defined using the Cantwell criteria)
  - Death of infant
  - Death of mother
  - Combined endpoint of maternal TB or maternal death
  - Combined endpoint of infant TB or infant death
  - Combined endpoint of maternal TB, maternal death, infant TB, or infant death

NOTE: TB endpoints and infant cause of death will be reviewed by a Secondary Endpoint Review Committee (SERC), which consists of maternal and pediatric TB specialists who may be

members of the study team. Refer to the Endpoint Review Process document for details of the review process. Appendix 100 will be the basis for adjudication of the TB endpoint by the SERC and is available in the CRF Appendix Codes section of the Frontier Science IMPAACT Portal; the web link to portal can be found in the MOP. Cantwell criteria for Congenital TB are in the MOP and will be collected on the P1078 CRF.

Deaths of enrolled women will receive external review by the IERC for adjudication of study treatment attribution and will also be reviewed by the SERC. The SERC will consider if the cause of death (COD) is due to unrecognized active TB (expected to be rare), from a known cause other than active TB, or from an unknown cause.

- **Occurrence of each of the following safety outcomes in HIV-infected women: during pregnancy up to: (i) delivery (antenpartum) and (ii) 12 weeks postpartum**
  - Grade  $\geq$  3 AEs possibly, probably, or definitely related to INH/Placebo for INH or permanent discontinuation of INH/Placebo for INH due to an adverse event
  - Grade  $\geq$  3 AEs (all-cause)
  - Hepatotoxicity possibly, probably, or definitely related to INH/Placebo for INH
  - Hepatotoxicity (all-cause)

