### **5.3.4 Laboratory Values**

- ALT: number (%) by grade; mean (s.d.), min, max, median (Q1-Q3)
- AST: number (%) by grade [PE6817]
- Total Bilirubin: number (%) by grade [PE6817]
- ANC (cells/ $\text{mm}^3$ ): number (%) by grade [PE6812]
- Hemoglobin (g/dL): number (%) by grade [PE6812]
- Platelet count (cells/ $\text{mm}^3$ ): number (%) by grade [PE6812]

Note: Grading will be based on Appendix III of protocol for ALT, AST and total bilirubin and by DAIDS Version 1.0 toxicity grade otherwise. Baseline laboratory evaluations were done at screening, except for ALT, which was done at screening and entry. Baseline ALT is calculated as the mean of screening and entry values if both are available.

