## 5.5 Maternal Hepatotoxicity

Validation: The analysis programs in this section will be validated, but not double-programmed.

- Table of grade 1, 2, 3, and 4 LFTs (ALT, AST, TBIL): number (%) by highest grade [PE6817]
- Table of hepatotoxicity by type, assuming protocol grading and DAIDS grading, separately: number (%) with Fisher's exact tests with mid-*p* adjustment (Lydersen et al, 2009, *Statistics in Medicine*) [PE6817]:
  - Grade 3 ALT (highest grade)
  - Grade 4 ALT (highest grade)
  - Grade 3 ALT, AST, or TBIL (highest grade)
  - Grade 4 ALT, AST, or TBIL (highest grade)
  - Grade  $\geq 2$  ALT and grade  $\geq 2$  TBIL
  - Grade  $\geq 2$  ALT with symptomatic clinical hepatitis
  - Any hepatotoxicity (defined as any of the above)

Note: Symptomatic clinical hepatitis will be identified based on blinded review (pooled over study arms) by selected protocol team members (at end of study follow-up and prior to data freezing for final analysis). Substitute direct bilirubin for TBIL for participants on atazanavir.

- Create the following by treatment arm and efavirenz use at entry, separately [PE6817, ADM0040]:
  - Peak ALT: min, max, mean (SD), median (Q1-Q3), Wilcoxon rank sum test
  - Table of participant ALT levels (U/L) at scheduled study visits by stage of pregnancy (weeks AP/PP): N, mean (s.d.), median (Q1-Q3)
  - Table with number (%) of participants by ALT grade at scheduled study visits and stage of pregnancy (weeks AP/PP)

- Plot of median (Q1,Q3) ALT level at scheduled study visits by stage of pregnancy (weeks AP/PP)
- Table of estimates (with 95% confidence intervals) of difference in incidence rates between arms, based on stratified Mantel-Haenszel estimates (primary) and simple proportions (sensitivity) at week 48 postpartum, for the following endpoints [STATUS,PE4005,TRAC]:
  - Any hepatotoxicity, possibly, probably, or definitely related to study treatment
  - Any hepatotoxicity, all cause
- Kaplan-Meier plot of time to endpoint from randomization date by study arm and by gestational age, with number of events and number at risk for the following endpoints
  - Any hepatotoxicity, possibly, probably, or definitely related to study treatment
  - Any hepatotoxicity, all cause
- Table of analysis of difference in endpoint rates between arms up to (i) delivery and (ii) 12 weeks postpartum, based on stratified Mantel-Haenszel estimates (primary) and simple proportions (sensitivity), for the following endpoints [STATUS,PE4005,TRAC]:

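### Section 5.5 tests peak ALT with no stated window; taken over all follow-up, it compares two arms that are each assigned 28 weeks of INH, so an effect common to both courses largely cancels

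*SAP*

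**What the plan says.** - **The test.** SAP 5.5 lists "Peak ALT: min, max, mean (SD), median (Q1-Q3), Wilcoxon rank sum test" under the instruction "Create the following by treatment arm and efavirenz use at entry, separately". It gives no start or end for the peak and no baseline term.
- **Exposure.** Under SAP 1.2 the immediate arm takes "Maternal INH at study entry for 28 weeks and then switched to placebo for INH until 40 weeks postpartum". The deferred arm takes placebo "until 12 weeks postpartum and then switched to INH for 28 weeks until 40 weeks postpartum". Women "will be followed up to 48 weeks postpartum".
- **The objective served.** Secondary objective 3 (2.2) covers safety and hepatotoxicity, "as well as evaluate risk factors for these outcomes, during pregnancy and immediate postpartum in women on immediate versus deferred INH therapy". Section 3.2 sets the matching windows for its binary safety outcomes: "during pregnancy up to: (i) delivery (antenpartum) and (ii) 12 weeks postpartum".
- **The rest of 5.5.** Related and all-cause hepatotoxicity are compared by stratified Mantel-Haenszel estimates at week 48, and again to delivery and to 12 weeks postpartum. ALT levels and grades are tabulated by visit and stage of pregnancy, and median ALT is plotted, all without a test.
- **Baseline.** Section 5.3.4 already derives a baseline: "Baseline ALT is calculated as the mean of screening and entry values if both are available".

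**The concern.** Peak ALT is the only continuous liver measure in 5.5 with a test between arms. If the peak is taken over all follow-up, a woman's maximum can fall in an INH course whichever arm she is in. The contrast is then between an early and a late course, not between INH and placebo. By assignment, only the time up to 12 weeks postpartum sets INH against placebo, and that is the period secondary objective 3 names. The binary hepatotoxicity endpoints are cut there; peak ALT is not.

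What is at stake is interpretation. A non-significant p-value for peak ALT, reported under hepatotoxicity without a label, could be taken as liver reassurance about INH in pregnancy. A test on the whole-study maximum cannot give that reassurance when the drug effect is similar in both courses.

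**Working it through.** The SAP gives no power, SD or detectable difference for peak ALT, so there is no planned figure to reproduce.

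**Step 1: exposure (SAP 1.2).** The immediate course is 28 weeks from entry. The deferred course is 40 − 12 = 28 weeks. Both lie within follow-up to 48 weeks postpartum.

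**Step 2: why a common effect cancels.** Write log ALT at a visit as *b* + *e* + δ × (on INH), where *b* is the woman's level, *e* is visit-to-visit noise and δ is the INH effect. If δ is the same in both courses, and each course has about the same number of ALT measurements, the maximum over all visits has nearly the same distribution in both arms. This holds whatever the size of δ.

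**Step 3: illustrative simulation.**
- From the SAP: 950 women randomized equally, so 475 per arm; entry at 14 to 34 weeks' gestation; the INH periods above; baseline ALT as the mean of two values.
- Assumed: entry gestation uniform, delivery at 40 weeks, ALT every 4 weeks, no dropout, full adherence, and log-normal ALT with between-/within-woman log SD of 0.4/0.3 or 0.5/0.4. INH multiplies ALT by a constant while on drug.
- Test: two-sided Wilcoxon at 0.05, 400 trials per scenario. The Monte Carlo standard error at 5% is √(0.05 × 0.95 / 400) ≈ 1.1 percentage points.

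Rejection rates without baseline adjustment (range over the two SD settings):

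| INH effect, pregnancy / postpartum | Whole follow-up | To 12 weeks postpartum | To delivery |
|---|---|---|---|
| none / none | 3.8% | 3.2-3.5% | 3.0% |
| 10% / 10% | 3.5% | 71.2-89.2% | 69.0-86.2% |
| 20% / 20% | 3.5% | 99.5-100% | 99.5-100% |
| 30% / 30% | 3.5-4.0% | 100% | 100% |
| 20% / 10% | 8.2-14.5% | 96.2-99.5% | 99.5-100% |
| 30% / 10% | 33.2-62.8% | 100% | 100% |
| 20% / none | 28.5-53.5% | 80.8-96.2% | 99.5-100% |
| 30% / none | 67.2-92.5% | 99.0-100% | 100% |
| 10% / 20% | 9.0-12.8% | 95.0-99.2% | 69.0-86.2% |
| 10% / 30% | 23.2-36.8% | 99.8-100% | 69.0-86.2% |

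In the last two rows the whole-follow-up median ratio (immediate / deferred) is 0.95-0.98. The immediate arm looks better although INH raised ALT in pregnancy.

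**Step 4: what baseline adds.** With a common 10% effect, adjusting for baseline ALT raises power to 97-100% (to 12 weeks postpartum) and 94-99% (to delivery). With no window, adjustment leaves rejection at about 5-6% for common effects of 10-30%. The window restores sensitivity to a common effect; baseline adds precision.

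**Step 5: what the windows leave out.** With delivery at 40 weeks, immediate INH ends at (entry week + 28 − 40) weeks postpartum: 2 for entry at 14 weeks, 12 for 24 and 22 for 34. For the latest entrants a cut at 12 weeks postpartum drops the last 22 − 12 = 10 weeks of the immediate course.

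**The case against.** The strongest reply is that peak ALT is not an endpoint. The windows in 3.2 belong to four binary safety outcomes, and hepatotoxicity is defined there by thresholds, so nothing obliges the SAP to window a supporting line in a report list. The pregnancy question is answered elsewhere in 5.5, by the Mantel-Haenszel differences to delivery and to 12 weeks postpartum, and the by-visit ALT outputs would show a shift while women are on drug. The whole-period peak also fits the main hypothesis, which compares starting IPT in pregnancy with deferring it, on an endpoint that runs to week 48. If INH raises ALT equally in both courses, no difference between strategies is the right answer.

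Most of this stands. There is no internal contradiction, and the whole-period peak is a valid strategy comparison. It does not remove the point: the window is still unstated, the by-visit outputs carry no test, and threshold endpoints do not test for an ALT shift below their cut-offs.

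A reader might infer three stronger things that the documents do not support:
- **That the SAP declares a whole-study window.** It declares none; that is only the natural reading.
- **That the test, or the trial, is blind to liver effects in pregnancy.** The test keeps partial power when the effect is confined to or clearly larger in pregnancy, and the windowed binary analyses are planned.
- **That leaving out baseline ALT biases the test or causes the cancellation.** Under randomization it costs precision only, and Step 4 shows that adjustment alone does not restore sensitivity to a common effect.

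**Conclusion.** The point holds as a gap in specification and a cheap improvement to a supportive analysis. Read over all follow-up, the peak-ALT test compares strategies and rejects at about its nominal level (3.5-4.0%) when INH raises ALT by a similar proportion in both courses. It can point the other way when the postpartum effect is the larger one. The primary analysis and the planned hepatotoxicity endpoints are unaffected.

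The cancellation follows from the equal courses and held for every common effect and SD tried. It does assume similar ALT sampling in the two courses. The power figures are illustrative: ALT variability, visit spacing, adherence, delivery time and effect sizes are all assumptions. Average shifts of 10-30% are also far smaller than the 3 × and 5 × ULN thresholds that define hepatotoxicity in 3.2, so a gain in power here is a gain in detecting a shift in ALT, not in detecting liver injury.

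**What to change.** In SAP 5.5:
1. State the window for peak ALT and say that it uses post-randomization values only.
2. Add peak ALT (i) from randomization to delivery and (ii) from randomization to 12 weeks postpartum. Compare arms by rank ANCOVA, or ANCOVA on log peak ALT, adjusting for the 5.3.4 baseline and the gestational-age stratum. Describe the adjustment as a precision gain. Say how women with no ALT in a window are handled.
3. Keep the whole-follow-up peak, labelled as a comparison of the two strategies.

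The cost is SAP wording and derived variables from the ALT data already cited there (PE6817), with no new data. The downsides are two more supportive secondary comparisons and, for late entrants, windows that do not cover the whole immediate INH course. That second limit should be stated next to the results.

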## **5.6 Peripheral Neuropathy**

Validation: The analysis programs in this section will be validated, but not double-programmed.

- Table with  $\geq$ grade 1 peripheral neuropathy: number (%) by highest grade [NE6056]
- Table of BPNS final score: min, max, mean (SD), median (Q1-Q3), Wilcoxon rank sum test [NE6056]

## **5.7 Maternal Mortality**

Validation: The analysis programs in this section will be validated, but not double-programmed.

- Listing of maternal deaths including public ID, treatment arm, weeks on study, stage of pregnancy, site assessment of primary COD and treatment attribution, and IERC treatment attribution [STATUS, PE1414, TRAC]
- Listing of maternal deaths including the following peak lab values: ALT, AST, total bilirubin, alkaline phosphatase, GGT, INR, total protein, and albumin [PE6812, PE6817]

## **5.8 Treatment Intolerance**

Validation: The analysis programs in this section will be validated, but not double-programmed.

- Table of treatment discontinuation: number (%) of enrolled women discontinuing study treatment prematurely (discontinued study treatment prior to week 40 postpartum, which is the end of study treatment period for both arms) by reason [PE4005]

- Table of permanent treatment discontinuation due to toxicity: number (%) of enrolled women discontinuing study treatment prematurely due to toxicity by type of toxicity [PE4005, TXW0221]
- Listing of participants who permanently discontinued study drug due to toxicity but did not have a grade 3 or higher AE related to study treatment, including: blinded ID; treatment arm, actual week of treatment discontinuation, and off-treatment reason [PE4005, TRAC]

## **5.9 Primary Endpoints and Analysis**

Validation: The analysis programs in this section will be validated, and primary analysis will be double-programmed.

- Cross-tabulation of participants with at least one adverse event at least possibly related to study treatment based on IERC assessment and participants with at least one adverse event at least possibly related to study treatment based on site assessment: number (%) [TRAC]
- Table of most severe safety outcome related to study treatment among participants experiencing primary safety endpoints: number (%) of each of the following [STATUS,PE4005,TRAC]:
  - Grade 3 AE related to study treatment
  - Grade 4 AE related to study treatment
  - Death related to study treatment
  - Permanent discontinuation of study treatment due to toxicity but no grade 3 or higher AE related to study treatment
- Table of primary analysis of difference in endpoint rates between arms, based on stratified Mantel-Haenszel estimates at week 48 postpartum (primary) and simple proportions (sensitivity), for the following endpoints [STATUS,PE4005,TRAC]:
  - Primary safety endpoint
  - Any Grade  $\geq 3$  AE (all cause)
- Table of per-protocol and as-treated sensitivity analyses of difference in endpoint rates between arms, based on stratified Mantel-Haenszel estimates at week 48 postpartum and simple proportions, for the following endpoints [STATUS,PE4005,TRAC]:
  - Primary safety endpoint
  - Any Grade  $\geq 3$  AE (all cause)
- Table of sensitivity analysis coding deaths of unknown cause and all deaths as primary endpoints (if death or a prior AE experienced by the participant who died were not already considered to be a primary endpoint)
- Kaplan-Meier plot of time to endpoint from randomization date by study arm and by gestational age, with number of events and number at risk for the following endpoints
  - Primary safety endpoint
  - Any Grade  $\geq 3$  AE (all cause)
- Table of analysis of difference in endpoint rates between arms up to (i) delivery and (ii) 12 weeks postpartum, based on stratified Mantel-Haenszel estimates (primary) and simple proportions (sensitivity), for the following endpoints [STATUS,PE4005,TRAC]:

- Primary safety endpoint
- Any Grade  $\geq 3$  AE (all cause)
- Multivariable Poisson regression model for the primary safety endpoint adjusted for treatment arm and the following baseline characteristics: maternal age, duration on HAART (from start date of HAART to randomization date), CD4 count, gestational age, IGRA positivity, and HBsAg serology status

Per NIH policy for Phase III and pivotal Phase II and IV studies, NIH requires primary analyses of treatment comparisons to be summarized by sex and by race and treatment interactions with sex and race to be tested. These analyses are required so do not represent multiple comparisons and are presented in the primary study analysis regardless of power issues. As P1078 maternal analyses are restricted to women, the primary analysis will be presented by race but not by sex.

- Table of primary analysis of difference in primary safety endpoint rates between arms, based on stratified Mantel-Haenszel estimates at week 48 postpartum, by race [STATUS,PE4005,TRAC]
- Logistic regression of the primary safety endpoint on the interaction term for treatment and race

## 5.10 *In Utero* Exposure and Infant Outcomes

Validation: The analysis programs in this section will be validated, but not double-programmed.

Note: Exact categorical tests (with mid-p adjustment for the case of Fisher's exact tests) will be employed to compare the difference in outcomes between arms.

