### **5.3.1 Demographics**

- Age (years): N, N missing, mean (s.d.), min, max, median (Q1-Q3); number (%) by age group (eg. <24, 24-<29, 29-<34,  $\geq$ 34) with years rounded down [STATUS]
- Self-reported race/ethnicity: number (%) by category [STATUS]
- Country: number (%) [STATUS]
- Gestational age (weeks) at entry: N, N missing, mean (s.d.), min, max, median (Q1-Q3); number (%) by category (14-<24, 24-34) [OBW0006]
  - Note: Gestational age is determined based on best available method, with methods prioritized as (i) ultrasound, (ii) last menstrual period, (iii) fundal height, and may

not match the level used for stratification if the site defined best available method differently.

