### **5.10.3 Summary of adverse pregnancy outcomes**

Note: The evaluations of small for gestational age, premature birth, low birth weight and congenital anomalies are based on live births. Multiple births with both live birth and stillbirth outcomes will be counted as pregnancies with stillbirths and other adverse pregnancy outcomes that may have been observed. Pregnancy outcome of induced abortion will be excluded from adverse pregnancy outcome summaries.

- Table with number (%) of pregnancies resulting in each of the following adverse pregnancy outcomes:
  - Fetal demise (stillbirth, spontaneous abortion)
  - Premature birth (<37 weeks gestation)
  - Low birth weight (<2,500 grams)
  - Congenital anomalies
  - Any adverse pregnancy outcome excluding congenital anomalies (defined as any of the above excluding congenital anomalies)
  - Any adverse pregnancy outcome (defined as any of the above)
- Table with number (%) of pregnancies resulting in each of the following severe adverse pregnancy outcomes:
  - Fetal demise (stillbirth, spontaneous abortion)
  - Premature birth (<34 weeks gestation)
  - Low birth weight (<1,500 grams)
  - Any severe adverse pregnancy outcome (defined as any of the above)

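### Section 5.10 compares pregnancy and infant outcomes without the entry gestational-age strata used for randomization; a stratified comparison, with results shown by stratum, would be a free improvement

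*SAP*

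**What the plan says.** SAP section 1.2 states the design: "Participants will be stratified based on gestational age at entry, and will be randomized in equal proportions to one of the following two groups". The baseline table in section 5.3.1 gives the categories: "number (%) by category (14-<24, 24-34) [OBW0006".

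That factor carries into the main rate comparisons. Stratified Mantel-Haenszel differences are specified for:
- the primary safety endpoint (sections 4.1 and 5.9);
- related and all-cause hepatotoxicity (section 5.5);
- maternal and infant TB and death (section 4.2 and, if event numbers allow, section 5.11).

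Section 5.10 covers secondary objective 1, the safety of in utero exposure. Its only statement on inference begins "Exact categorical tests (with mid-p adjustment for the case of" and ends by naming Fisher's test and a comparison between arms. Sections 5.10.1 to 5.10.4 and the infant safety subsection add no strata, no stratified estimate or interval, and no table by entry gestational age. The severe outcomes in section 5.10.3 include "Premature birth (<34 weeks gestation").

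**The concern.** The immediate arm starts INH at entry, and the deferred arm has no planned INH until 12 weeks postpartum. Entry gestational age therefore fixes how long a fetus in the immediate arm is exposed. It also fixes how much of the preterm-birth risk window remains. The outcomes in section 5.10 depend on this factor at least as much as the maternal outcomes do, yet it is left out here and no reason is given.

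Two things are at stake. First, a test that ignores a stratification factor used in the randomization gives up a little precision. Second, and more important in a safety comparison, a single pooled result cannot show whether any fetal harm lies among women exposed from the second trimester.

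**Working it through.** **Inputs.** From SAP section 1.2: target 950 women, equal allocation (475 per arm), entry from 14 weeks to 34 weeks 6 days. From section 5.3.1: categories 14 to <24 and 24 to 34 weeks, taken here to be the randomization strata. The SAP gives no outcome rates, stratum shares or power for section 5.10, so there is no stated figure to reproduce. Assumed: delivery at 40 weeks, two-sided 0.05, 30% or 50% of women in the early stratum, and the rates shown below.

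**1. Exposure and risk windows.** Exposure = 40 − entry week. Risk window for birth before week *w* = max(0, *w* − entry week).

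| Entry | Weeks of fetal INH (immediate arm) | Weeks at risk, birth <37 | Weeks at risk, birth <34 |
|---|---|---|---|
| 14w0d | 26 | 23 | 20 |
| 24w0d | 16 | 13 | 10 |
| 34w0d | 6 | 3 | 0 |
| 34w6d | about 5 | about 2 | 0 |

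If entry were uniform over 14 to 35 weeks, mean exposure would be 40 − 19 = 21 weeks in the early stratum and 40 − 29.5 = 10.5 weeks in the late one.

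**2. Precision.** Ratio of within-stratum to pooled variance, with equal-sized strata:
- Risks 15% and 8%: (0.15×0.85 + 0.08×0.92)/2 ÷ (0.115×0.885) = 0.10055/0.101775 = 0.988.
- Risks 20% and 10%: (0.16 + 0.09)/2 ÷ (0.15×0.85) = 0.125/0.1275 = 0.980.

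The gain is 1 to 2% of variance.

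**3. Simulation.** 20,000 runs per scenario, arms balanced within strata, common odds ratio 1.8 for power. The pooled Fisher mid-p test is compared with the large-sample Cochran-Mantel-Haenszel (CMH) test.

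| Early share | Control rate, early/late | Type I error, pooled / stratified | Power, pooled / stratified |
|---|---|---|---|
| 30% | 4% / 0% | 0.037 / 0.045 | 0.17 / 0.19 |
| 30% | 14% / 10% | 0.049 / 0.050 | 0.89 / 0.89 |
| 30% | 20% / 6% | 0.045 / 0.050 | 0.83 / 0.85 |
| 30% | 30% / 5% | 0.036 / 0.050 | 0.82 / 0.86 |
| 50% | 4% / 0% | 0.045 / 0.052 | 0.28 / 0.29 |
| 50% | 14% / 10% | 0.051 / 0.052 | 0.90 / 0.91 |
| 50% | 20% / 6% | 0.045 / 0.050 | 0.90 / 0.91 |
| 50% | 30% / 5% | 0.037 / 0.049 | 0.91 / 0.93 |

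The 0.036 can be checked by hand. With 30% early and rates 30%/5%, the pooled risk is 0.125 and its variance 0.125×0.875 = 0.1094. The within-stratum variance is 0.3×0.21 + 0.7×0.0475 = 0.0963, a ratio of 0.88. The effective critical value is 1.96/√0.88 = 2.09, a two-sided error of about 0.037.

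In the 4%/0% row with 30% early, the same ratio is 0.01152/0.011856 = 0.972, which predicts about 0.047. The rest of the shortfall to 0.037 is the discreteness of an exact test with few events, and stratifying would not remove that.

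**4. Effect confined to early entrants.** Assume 12% rising to 22% in the early stratum and 10% in both arms in the late stratum.

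| Early share | Overall difference | Power, pooled | Power, CMH | Power, early stratum alone |
|---|---|---|---|---|
| 30% | 0.3×10 = 3 points | 0.29 | 0.29 | 0.61 |
| 50% | 0.5×10 = 5 points | 0.62 | 0.63 | 0.83 |

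Stratifying the test leaves this problem where it was. Showing the strata does address it.

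**The case against.** The strongest reply is that section 5.10 follows a pattern in the SAP: stratified Mantel-Haenszel for endpoint-rate differences, exact tests for tables of counts. This has substance. A reader might infer that section 5.10 is the only unstratified comparison, but hepatotoxicity by type (section 5.5) uses the same Fisher mid-p test, and peak ALT (section 5.5) and the neuropathy score (section 5.6) use Wilcoxon tests without strata. Infant TB and infant death do have stratified analyses. The contrast is therefore with the main rate differences only.

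Four stronger readings are tempting, and the SAP does not support them:

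- **That the pooled test is biased or too liberal.** Randomization within strata balances entry age between arms. The simulated type I error was 0.036 to 0.051.
- **That women entered at 34 weeks should leave the denominator for birth before 34 weeks.** Section 5.10.2 takes gestational age at birth first from the newborn exam, whereas section 5.3.1 takes entry age from ultrasound, last menstrual period or fundal height. A woman entered at 34 weeks can thus have a recorded birth before 34 weeks, and exclusion could discard that event. It would also separate this component's denominator from that of the severe-outcome composite.
- **That twins are counted as independent in the pregnancy outcomes.** Section 5.10.3 counts pregnancies and says how discordant multiple births are handled. The infant tables do not state their unit, so treating them as wrong would be inference.
- **That a CMH test would reveal harm limited to early entrants.** Step 4 shows that it would not.

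The objection that the gain in the test is small also stands.

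**Conclusion.** The point holds as a minor one. Section 5.10 leaves out a randomization factor that the SAP uses for its main rate differences and that bears directly on fetal exposure and preterm risk. The planned test is valid. The cost is 1 to 2% of variance in step 2, 0 to 4 points of power in step 3, and some conservatism where risks differ strongly between strata. The larger weakness is that nothing is reported by exposure window, so an effect confined to early entrants would be diluted to 3 or 5 points from 10 in the example.

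All rates, effects, stratum shares and the 40-week delivery are assumptions. The power figures for the stratified test come from its large-sample form, so an exact mid-p version may gain slightly less for rare outcomes.

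**What to change.** In section 5.10:

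1. Compare arms with an exact (mid-p) Cochran-Mantel-Haenszel test stratified by entry gestational age (14 to <24, 24 to 34 weeks).
2. Report the stratified Mantel-Haenszel risk difference with a 95% CI, as the SAP does elsewhere.
3. Tabulate each adverse pregnancy outcome by arm within entry stratum, as description rather than as further tests.
4. Use the same stratum variable as the primary analysis, because section 5.3.1 notes that derived entry age may not match the level used for stratification.

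The cost is a few lines of SAP text, one strata term in the programs and one extra table layout. Entry gestational age is already collected. Denominators and the counting of pregnancies stay as planned.
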